5.2.4 Electrocardiogram

The 12-lead ECGs must be administered by a qualified technologist and results will be recorded as scheduled in the [flowchart](#). The investigator or a designee will evaluate whether the ECG is normal or abnormal and assess clinical relevance. ECGs may be repeated for quality reasons and a repeated recording used for analysis.

Additional ECGs may be recorded for safety reasons. Dated and signed printouts of ECG with findings should be documented in patient's medical record.

Clinically relevant abnormal findings will be reported as adverse events and will be followed up and/or treated as medically appropriate.

5.2.5 Other safety parameters

Local tolerability at the administration site of the subcutaneous injection will be assessed by the investigator at the specified visits as noted in the [Flow Chart](#).

Local tolerability at the administration site of spesolimab will be assessed by the investigator during the study drug administration visit and at the time of AE assessment by questioning retrospectively since the last visit. Any observed local tolerability reactions like "swelling", "induration", "heat", "redness", "pain", or any other findings should be reported as an adverse event in the eCRF.

5.2.6 Assessment of adverse events

5.2.6.1 Definitions of AEs

5.2.6.1.1 Adverse event

An AE is defined as any untoward medical occurrence in a patient or clinical investigation subject administered a medicinal product and which does not necessarily have to have a causal relationship with this treatment.

An AE can therefore be any unfavourable and unintended sign (including an abnormal laboratory finding), symptom, or disease temporally associated with the use of a medicinal product, whether or not considered related to the medicinal product.

The following should also be recorded as an AE in the CRF and BI SAE form (if applicable):

- Worsening of the underlying disease or of other pre-existing conditions
- Changes in vital signs, ECG, physical examination and laboratory test results, if they are judged clinically relevant by the investigator.

If such abnormalities already exist prior to trial inclusion, they will be considered as baseline conditions and should be collected in the eCRF only. However, if these abnormalities are AEs of the parent trial and still ongoing after first dose in extension trial, they should not be recorded as baseline conditions. In such situations [section 5.2.6.2](#) should be followed.

5.2.6.1.2 Serious adverse event

A serious adverse event (SAE) is defined as any AE which fulfils at least one of the following criteria:

- results in death;
- is life-threatening, which refers to an event in which the patient was at risk of death at the time of the event; it does not refer to an event that hypothetically might have caused death if more severe;
- requires inpatient hospitalisation or prolongation of existing hospitalisation
- results in persistent or significant disability or incapacity;
- is a congenital anomaly / birth defect;
- is deemed serious for any other reason if it is an important medical event when based on appropriate medical judgement which may jeopardise the patient and may require medical or surgical intervention to prevent one of the other outcomes listed in the above definitions. Examples of such events are intensive treatment in an emergency room or at home for allergic bronchospasm, blood dyscrasias or convulsions that do not result in hospitalisation or development of dependency or abuse.

5.2.6.1.3 AEs considered “Always Serious”

In accordance with the European Medicines Agency initiative on Important Medical Events, Boehringer Ingelheim has set up a list of AEs, which by their nature, can always be

considered to be “serious” even though they may not have met the criteria of an SAE as defined above.

The latest list of “Always Serious AEs” can be found in the eDC system. A copy of the latest list of “Always Serious AEs” will be provided upon request. These events should always be reported as SAEs as described in [Section 5.2.6.2](#).

Cancers of new histology and exacerbations of existing cancer must be classified as a serious event regardless of the time since discontinuation of the drug and must be reported as described in [Section 5.2.6](#) subsections “AE Collection” and “AE reporting to sponsor and timelines”.

5.2.6.1.4 Adverse events of special interest

The term adverse events of special interest (AESI) relates to any specific AE that has been identified at the project level as being of particular concern for prospective safety monitoring and safety assessment within this trial, e.g. the potential for AEs based on knowledge from other compounds in the same class. AESIs need to be reported to the sponsor’s Pharmacovigilance Department within the same timeframe that applies to SAEs (see [Section 5.2.6.2.2](#)).

The following are considered as AESIs:

Hepatic injury

A hepatic injury is defined by the following alterations of hepatic laboratory parameters:

- an elevation of AST (Aspartate Aminotransferase) and/or ALT (Alanine Aminotransferase) ≥ 3 fold ULN combined with an elevation of total bilirubin ≥ 2 fold ULN measured in the same blood draw sample, and/or
- aminotransferase (ALT, and/or AST) elevations ≥ 10 fold ULN.

These lab findings constitute a hepatic injury alert and the patients showing these lab abnormalities need to be followed up according to the “DILI checklist” provided in the ISF. In case of clinical symptoms of hepatic injury (icterus, unexplained encephalopathy, unexplained coagulopathy, right upper quadrant abdominal pain, etc.) without lab results (ALT, AST, total bilirubin) available, the investigator should make sure these parameters are analysed, if necessary in an unscheduled blood test. Should the results meet the criteria of hepatic injury alert, the procedures described in the DILI checklist should be followed.

Systemic hypersensitivity including infusion reaction and anaphylactic reaction

Any suspicion of severe infusion reaction systemic / hypersensitivity reaction and of any potential cases of anaphylaxis should be defined and assessed using the criteria in [Appendix 10.8 \(R11-4890\)](#). All confirmed and suspected cases of systemic hypersensitivity, including infusion reaction and anaphylactic reaction, will be reported as AESIs.

Any observed local tolerability reactions like “swelling”, “induration”, “heat”, “redness”, “pain”, or any other findings should be reported as an adverse event in the eCRF.

In case of an infusion reaction monitor the patient per standard of care, grade the intensity of the reaction according to RCTC grading (see ISF) and proceed as described in [Section 4.2.1](#). Also draw plasma sample for IgE and ADA (anti-drug antibodies), as detailed in the CTP [section 5.2.3](#) and the lab manual.

Severe infections (according to RCTC grading in ISF)

Opportunistic and mycobacterium tuberculosis infections

These include pneumocystis jirovecii, BK virus disease including PVAN, CMV, post-transplant lymphoproliferative disorder (EBV), progressive multifocal leucoencephalopathy, bartonellosis (disseminated only), blastomycosis, toxoplasmosis, coccidioidomycosis, histoplasmosis, aspergillosis (invasive only), candidiasis (invasive or pharyngeal), cryptococcosis, other invasive fungi (mucormycosis (zygomycosis, rhizopus, mucor, lichtheimia), scedosporium/pseudallescheria boydii, fusarium), legionellosis, listeria monocytogenes (invasive only), tuberculosis, nocardiosis, non-tuberculous mycobacterium, salmonellosis (invasive only), HBV reactivation, herpes simplex (invasive only), herpes zoster, strongyloides (hyperinfection syndrome and disseminated forms only), paracoccidioides, penicillium marneffei, sporothrix schenckii, cryptosporidium species (chronic only), microsporidiosis, leishmaniasis (visceral only), trypanosoma cruzi infection (Chagas' disease) (disseminated only), campylobacteriosis (invasive only), shigellosis (invasive only), vibriosis (invasive due to vibrio vulnificus), HCV progression ([R17-2617](#))

5.2.6.1.5 Intensity (severity) of AEs

The intensity grading of AEs will be performed according to Rheumatology Common Toxicity Criteria (RCTC) Version 2.0 developed by [REDACTED] ([Appendix 10.6](#), and available in ISF) ([R13-3515](#)). Intensity options are:

Grade 1	mild
Grade 2	moderate
Grade 3	severe
Grade 4	life-threatening

5.2.6.1.6 Causal relationship of AEs

Medical judgement should be used to determine whether there is a reasonable possibility of a causal relationship between the adverse event and the given study treatment, considering all relevant factors, including pattern of reaction, temporal relationship, de-challenge or re-challenge, confounding factors such as concomitant medication, concomitant diseases and relevant history.

Arguments that may suggest that there is a reasonable possibility of a causal relationship could be:

- The event is consistent with the known pharmacology of the drug.

- The event is known to be caused by or attributed to the drug class.
- A plausible time to onset of the event relative to the time of drug exposure.
- Evidence that the event is reproducible when the drug is re-introduced.
- No medically sound alternative aetiologies that could explain the event (e.g. pre-existing or concomitant diseases, or co-medications).
- The event is typically drug-related and infrequent in the general population not exposed to drugs (e.g. Stevens-Johnson syndrome).
- An indication of dose-response (i.e., greater effect size if the dose is increased, smaller effect size if dose is reduced).

Arguments that may suggest that there is no reasonable possibility of a causal relationship could be:

- No plausible time to onset of the event relative to the time of drug exposure is evident (e.g. pre-treatment cases, diagnosis of cancer or chronic disease within days / weeks of drug administration; an allergic reaction weeks after discontinuation of the drug concerned).
- Continuation of the event despite the withdrawal of the medication, taking into account the pharmacological properties of the compound (e.g. after 5 half-lives). Of note, this criterion may not be applicable to events whose time course is prolonged despite removing the original trigger.
- Additional arguments amongst those stated before, like alternative explanation (e.g. situations where other drugs or underlying diseases appear to provide a more likely explanation for the observed event than the drug concerned).
- Disappearance of the event even though the trial drug treatment continues or remains unchanged.

5.2.6.2 Adverse event collection and reporting

5.2.6.2.1 AE Collection

The investigator shall maintain and keep detailed records of all AEs in the patient files. The following must be collected and documented on the appropriate CRF(s) by the investigator (special notes on SAE form reporting where needed):

- From the time of first dose of trial drug administration in the extension trial until the individual patient's end of trial:
all AEs (serious and non-serious) and all AESIs.
- All AEs that started in the parent trial (onset date in parent trial) and are still ongoing after 1st IMP administration in the extension trial:
 - Re-record the AE in the extension trial eCRF with the same information as it was recorded in the parent trial.
 - Should the AE end during the course of the extension trial,
⇒ update both - the extension trial eCRF and the parent trial eCRF. If the parent trial is already locked, update only the extension trial eCRF. In this case the

update for the parent trial will be handled outside of the eCRF of the parent trial.

- However, concerning reporting on the SAE form (if applicable), the follow-up report will still be sent on the parent trial SAE form, no new SAE form is to be completed for the extension trial.
- If the intensity of an ongoing AE changes after 1st IMP administration in the extension trial:
 - ⇒ update both - the extension trial eCRF and the parent trial eCRF- with the end date for the initial/previous intensity. If the parent trial is already locked, update only the extension trial eCRF. In this case the update for the parent trial will be handled outside of the eCRF of the parent trial.
 - ⇒ The AE with the new intensity will be handled as new event; this means it is only recorded in the extension trial eCRF.
 - Example: If the intensity increased then the new AE name/term should contain “Worsening of...” or “Exacerbation of...”

Considerations for reporting on the SAE form, when intensity change qualifies as worsening/exacerbation of an event that had already been reported on the SAE form:

- corresponding follow up report to be sent on the parent trial SAE form with date of worsening as event end date.
- extension trial SAE form to be sent as initial report for the extension trial for new event “Worsening/Exacerbation of....” with date of worsening as onset date.

Considerations for reporting on the SAE form, when intensity change qualifies as worsening/exacerbation of an event and requires for the first time reporting on the SAE form (meeting for the first time seriousness/AESI criteria):

- only extension trial SAE form to be sent - as initial report for the extension trial for new event “worsening/exacerbation of....” with date of worsening as onset date.

- All AEs with an end date **before** the 1st IMP administration in the extension trial, even if Informed Consent of the extension trial was already signed:
 - Record only in the eCRF of the parent trial.
 - In case of an AE reportable on the SAE form, send the update only on the SAE form of the parent trial.
 - Do not re-record in the extension trial eCRF, do not complete a new SAE form for the extension trial.
- After the EoS visit in the extension trial:

The investigator does not need to actively monitor the patient for new AEs but should

only report any occurrence of cancer (cancer of new histology, exacerbations of existing cancer, if applicable) and trial treatment related SAEs and trial treatment related AESIs of which the investigator may become aware of by any means of communication, e.g. phone call. Those AEs should be reported on the BI SAE form (see [Section 5.2.6.2.2](#)) for the extension trial, but not on the CRF (neither on CRF for extension nor for partent trial).

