3.3.2 Inclusion criteria

Each patient must meet all of the following inclusion criteria to be included into the trial:

1. Patient older than 18 years
2. Has completed all treatments (placebo or active treatment) and the EOT visit in the parent induction trial in fistulising CD and is willing and able to continue treatment in 1368-0007.

3. Has obtained an individual health benefit, per investigator judgement (such as fistula response or remission or other clinical improvement), from treatment in the parent trial.
4. Signed and dated written informed consent for 1368-0007 in accordance with GCP and local legislation prior to admission into the trial.
5. Women of childbearing potential (WOCBP) must be ready to use highly effective methods of birth control per ICH M3 (R2) that result in a low failure rate of less than 1% per year when used consistently and correctly. A list of contraception methods meeting these criteria is provided in the patient information.

Note: A woman is considered of childbearing potential (WOCBP), i.e. fertile, following menarche and until becoming postmenopausal unless permanently sterile. Permanent sterilisation methods include hysterectomy, bilateral salpingectomy and bilateral oophorectomy. Tubal ligation is NOT a method of permanent sterilisation. A postmenopausal state is defined as no menses for 12 months without an alternative medical cause.

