7.2.2 Primary endpoint analyses

Refer to [Section 2.1.2](#) for the description of the primary endpoint. The primary analyses will be descriptive in nature. All treated patients will be included in the primary analyses. No hypothesis testing is planned.

Adverse events will be coded using the Medical Dictionary for Drug Regulatory Activities (MedDRA). Standard BI summary tables and listings will be produced. All adverse events with an onset between start of treatment of this trial and end of the residual effect period

(REP), a period of 16 weeks after the last dose of trial medication, will be assigned to the on-treatment period for evaluation.

Adverse events that start before first drug intake and deteriorate under treatment will also be considered as 'treatment-emergent'. For all patients who, due to a fistula relapse received the intensified treatment with spesolimab, safety assessments including adverse events, laboratories, vital signs, etc., which occurred subsequent to such intake will be excluded from presentations according to the planned treatment; these data will, however, be included in summaries where all data after any use of spesolimab are displayed.

Exposure-adjusted adverse event incidence rates will be calculated using the following approach:

The incidence rate (per 100 patient years) of a selected adverse event (also known as the incidence density rate or person-time incidence rate) is defined as the number of patients experiencing the adverse event during the time at risk divided by the total time of patients at risk to contribute an event to the analysis multiplied by 100, where:

$$\text{Time at risk (in subject years)} = ((\text{date of onset of AE} - \text{study drug start date}) + 1) / 365.25$$

The study drug start date refers to the start date of this trial. If, for a patient, no treatment emergent adverse event occurred, then the time at risk will be censored at the minimum of: date of death; drug stop date + 112 days; start date of CD inflammatory flare or fistula relapse treatment with spesolimab; last contact date; or, date of database snapshot if an interim analysis was performed.

For each AE, the incidence rate will therefore be calculated as:

$$\text{Incidence rate} = 100 * \text{number of patients with TEAE} / \text{Total TEAE-specific time at risk.}$$

Exact 95% confidence intervals around the observed AE incidence rate will also be provided.

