7.8.1 Adverse events

AEs will be coded with the most recent version of MedDRA.

The analysis of AEs will be descriptive in nature. All analyses of AEs will be based on the number of patients with AEs and not on the number of AEs. System organ classes (if applicable) will be sorted according to the standard sort order specified by the EMA. Preferred terms (if applicable) will be sorted by total frequency (within system organ class).

For further details on summarization of AE data, please refer to "Analysis and Presentation of Adverse Event Data from Clinical Trials" (4) [KM Asset BI-KMED-BDS-HTG-0041] and "Handling of missing and incomplete AE dates" (3) [KM Asset BI-KMED-BDS-HTG-0035].

The analysis of AEs will be based on the concept of treatment emergent AEs. This means that all AEs will be assigned to either the screening period, the applicable on-treatment period, or the off-treatment period (i.e. follow-up) as defined in Section 6.1. Since only the start date of an AE is collected (without start time), any AE which occurs on the same day as the first maintenance treatment will be assigned to the respective on-treatment period.

Refer to CTP Section 7.2.2 for a description of the calculation of exposure-adjusted adverse event incidence rates (per the primary endpoint).

The AE summaries described below will be produced for the following treatment periods:

• The overall maintenance period [based on the SAF]

An overall summary of AEs will be presented. This overall summary will include the class of AESIs. Refer to CTP Section 5.2.6.1.4 for a description of what is considered as an AESI.

The investigator identified AESI will be captured from the eCRF and reported in the "Investigator reported AESI" table. In addition, user defined adverse event categories (UDAEC) identified through specific search criteria will be reported separately; the UDAEC applicable to this trial are stored centrally and will be referenced for this presentation.

Adverse Events classified as 'other significant' will be reported using an adaptation of the ICH E3 (6) and will include those non-serious and non-significant AEs which were reported with 'action taken = drug withdrawn' or 'action taken = reduced'.

Table 7.8.1: 1 Project MEDDRA search criteria for User Defined Adverse Events Categories (UDAEC)

User-defined AE category			
Label	Description		
Infections ALL	Combined search strategy based on the individual UDAECs for infections described below		

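### A carried-over parent-trial AE that first turns serious, an AESI or treatment-stopping at an unchanged intensity can be missed in the extension's safety summary tables

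*Protocol*

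**What the plan says.** **Collection (Protocol 5.2.6.2.1).** An AE that began in the parent trial and is ongoing after the first extension dose is copied across: "Re-record the AE in the extension trial eCRF with the same information as it was recorded in the parent trial". For SAE follow-up of such an event, the report stays on the parent form and "no new SAE form is to be completed for the extension trial". The section then gives rules for two later changes only: the AE ends, or its grade moves ("If the intensity of an ongoing AE changes after 1st IMP administration in the extension trial"). Only the second makes a new record: "The AE with the new intensity will be handled as new event; this means it is only recorded in the extension trial eCRF". First-time seriousness or AESI status is foreseen, but only "when intensity change qualifies as worsening/exacerbation of an event and requires for the first time reporting on the SAE form".

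**Treatment-emergence (Protocol 7.2.2).** AEs with onset between the first extension dose and 16 weeks after the last dose are on-treatment. In addition, "Adverse events that start before first drug intake and deteriorate under treatment will also be considered as" treatment-emergent. Protocol 7.2.5 refers to this section for the complete definition.

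**Allocation (SAP 6.1 and 7.8.1).** The on-treatment period opens at the first s.c. maintenance dose. For AEs, "This means that all AEs will be assigned to either the screening period, the applicable on-treatment period, or the off-treatment period". AE summaries are produced for the overall maintenance period only, with separate tables for SAEs, AESIs and AEs leading to discontinuation. For the incidence-rate calculation the SAP points back to Protocol 7.2.2, but it does not repeat the deterioration clause in its allocation rule.

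**The concern.** Seriousness (Protocol 5.2.6.1.2) and intensity (5.2.6.1.5) are separate attributes. A patient can be hospitalised for a carried-over AE, or taken off drug because of it, without any change of grade. The collection rule ties the creation of a dated extension record to grade alone. In the remaining cases the only record is the copied one, whose onset date precedes the extension.

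Safety is the primary objective of this trial. The tables at stake are those a safety reader turns to first: SAEs, AESIs and AEs leading to discontinuation on open-label spesolimab. With at most about 20 patients, one omitted case is visible in any of them.

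**Working it through.** The documents give no figure on this point, so there is none to reproduce. The check sets the rules side by side, then applies the plan's own time-at-risk formula.

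**Step 1. What happens to a carried-over AE after the first extension dose**

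| Change | Rule in Protocol 5.2.6.2.1 | Onset date used | Place under SAP 6.1 / 7.8.1 |
|---|---|---|---|
| AE ends | End date updated | Parent | Before on-treatment period |
| Intensity changes, up or down | New extension event | Date of change | On-treatment |
| First serious or AESI, with an intensity change that counts as worsening | New event, extension SAE form | Date of worsening | On-treatment |
| First serious, or AESI not defined by AE grade, grade unchanged | None stated | Parent | Before on-treatment period |
| Leads to drug withdrawal, grade unchanged | None stated | Parent | Before on-treatment period |
| Fatal, already at grade 4 | No new-event rule | Parent | Before on-treatment period |

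The last three rows are the gap. SAP 6.1 starts the screening period at consent or the first screening procedure, so an onset before that date precedes even the screening period.

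**Step 2. Does the deterioration clause repair it?** Suppose the clause in Protocol 7.2.2 is applied and the copied record is counted as treatment-emergent. The same section defines

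time at risk = ((AE onset date − extension drug start date) + 1) / 365.25.

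For a parent onset d days before the first extension dose this is (−d + 1)/365.25:

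- d = 1: 0/365.25 = 0 years
- d = 14: −13/365.25 = −0.036 years
- d = 28: −27/365.25 = −0.074 years
- d = 168: −167/365.25 = −0.457 years

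The values of d are illustrative. As written, the event is either left out by date or enters with an invalid time at risk. A date of deterioration would resolve this, but neither document provides for one.

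**Step 3. Size of one omitted patient.** Inputs: 20 patients (the upper limit in Protocol 7.5), with one such patient assumed.

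- Proportion: 1/20 = 5.0%. Clopper-Pearson 95% CIs are 0 to 16.8% for 0/20 and 0.1 to 24.9% for 1/20.
- Rate, if all 20 contributed 144 weeks (the upper end of the exposure categories in SAP 7.7): 20 × 144 × 7/365.25 = 55.2 patient-years. The rate moves from 0 (exact 95% CI 0 to 6.68) to 1.81 (0.05 to 10.09) per 100 patient-years.
- Rate, if all 20 contributed 352 weeks: 20 × 352 × 7/365.25 = 134.9 patient-years. The rate moves from 0 (0 to 2.73) to 0.74 (0.02 to 4.13).

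Both follow-up totals are assumptions, and they ignore that time at risk stops at the event. The 352-week case is an outer bound, because the SAP describes a discontinued trial.

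**The case against.** The strongest reply is Protocol 7.2.2. Its deterioration clause is not restricted to intensity, the SAP rests on that section, and SAP section 4 lists no change to the definition. An AE that turns serious is naturally read as having deteriorated. This stands against the inference that the plan excludes such events: it does not. The clause still has no definition, no date and no counterpart in the SAP allocation, so programming that follows the allocation rule literally can miss the event.

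A second reply is that copying the parent information describes the record at entry, and nothing forbids later updates of seriousness, outcome or action taken. That is fair, and the eCRF instructions and cited internal standards are not available to check. Updating those fields would not move the onset date.

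Several stronger readings are tempting and are not supported:

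- **Newly serious events are filed under the parent trial, even under its placebo arm.** Placebo patients may enter ("Has completed all treatments (placebo or active treatment) and the EOT visit in the parent induction trial"), but the parent-form rule concerns follow-up reports, which presuppose an earlier report. For an event first serious in the extension at an unchanged grade, the text does not name a form. Protocol 5.2.6.2.2 still requires SAEs and AESIs to be reported within 24 hours.
- **Deaths and severe infections are lost.** Grade 4 is life-threatening, so a fatal course would normally pass through a grade change unless the AE was already at grade 4. The severe-infection AESI is defined by grade, so reaching it creates a new event.
- **Withdrawals disappear.** SAP 6.6.1 reports withdrawal reasons from the eCRF, SAP section 7 lists individual data including off-treatment values, and SAP 7.8.1 adds AE listings. Only the AE-based summary table is exposed.
- **The recording rule can only lower extension counts.** A fall in intensity also creates a new extension event, which works the other way.

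**Conclusion.** The point holds in a limited form. A carried-over AE that first becomes serious, first meets an AESI criterion not defined by AE grade, or leads to drug withdrawal at an unchanged grade has no rule that gives it an extension onset date. The same applies to a fatal AE already at grade 4. The date-based allocation can then leave it out of the extension SAE, AESI and AE-leading-to-discontinuation tables. The deterioration clause shows that the intention is to count such events, but it cannot be applied as written. This is an unresolved conflict between collection, definition and allocation, not a stated exclusion.

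One such patient is worth 5 percentage points in a 20-patient table. The intervals with and without the case overlap heavily, and the analysis is descriptive, so no formal conclusion turns on it. What matters is whether an on-treatment SAE appears in the summary or only in a listing. The size assumes 20 treated patients and one event; the documents do not say whether any such event occurred.

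**What to change.** **SAP 7.8.1 (the priority, because version 2.0 precedes final database lock).** State that a carried-over AE is treatment-emergent if, after the first extension dose, it first meets a seriousness or AESI criterion, has a fatal outcome, or leads to withdrawal of trial drug, whether or not intensity changed. Use the date of that change as onset for both period allocation and time at risk.

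**Protocol 5.2.6.2.1.** Align the collection rule: such a change is recorded as a new extension event with that date, on the extension SAE form when it first becomes reportable. With the trial ending early this may govern few further records, so the SAP rule carries most of the weight.

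**Before final lock.** Reconcile SAE reports of rolled-over patients dated after the first extension dose against the extension database.

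**Cost.** A sentence or two in the SAP, one bullet in the protocol and a query covering about 20 patients. The downside is a small amount of extra data work, and extension SAE, AESI and discontinuation counts may rise slightly.
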